6.3 Participant numbering, treatment assignment, randomization

6.3.1 Participant numbering

Each participant is identified in the study by a Participant Number (Participant No.), that is assigned when the participant is enrolled for prescreening (if applicable) or screening and is retained for the participant throughout his/her participation in the trial. A new Participant No. will be assigned at every subsequent enrollment if the participant is re-screened. The Participant No. consists of the Center Number (Center No.) (as assigned by Novartis to the investigative site) with a sequential participant number suffixed to it, so that each

participant's participation is numbered uniquely across the entire database. Upon signing the informed consent form, the participant is assigned to the next sequential Participant No. available.

The investigator or designated staff will contact the Interactive Response Technology (IRT) and provide the requested identifying information to register the participant. Once assigned, the participant No. must not be reused for any other participant and the participant No. for that individual must not be changed unless the participant is re-screened. If the participant fails to be randomized or start treatment for any reason, the reason will be entered into the appropriate eCRF page and IRT should be notified as soon as possible. Re-screening is allowed once for participants that were initially screen failures for any reason. All eligibility criteria must be re-checked and met prior to enrollment of the participant into the study. A new participant No. should be assigned for all re-screened participants.

A new ICF will need to be signed if the investigator chooses to re-screen the participant after a participant has screen failed, and the participant will be assigned a new Participant No.

6.3.2 Treatment assignment, randomization

This phase Ib/II trial is an open label study.

- In the Part 1 (safety run-in part), the study is non-randomized, and participants will be treated with sabatolimab in monotherapy
- In the Part 2, adult participants will be randomized to one of the two cohorts: combination cohort (Cohort 3 with sabatolimab + azacitidine as study treatment) and expansion monotherapy cohort (Cohort 4 with sabatolimab monotherapy as study treatment). The randomization ratio will depend on the number of participants from the safety-run in part (Part 1) already treated with sabatolimab at the selected dose level for expansion. If the sabatolimab dose selected for expansion is the 800 mg dose level and if 12 participants are included in the safety run-in part at that dose level, participants will be randomized in a 1:1.5 ratio to one of the two adult cohorts in Part 2. Thus, 25 participants will be treated with sabatolimab in monotherapy at the selected dose level (12 participants from the safety run-in cohorts and 13 participants from the expansion monotherapy cohort) and 20 participants will be treated with sabatolimab at the selected dose given in combination with azacitidine (20 participants from the combination cohort).
- In Part 2, adolescent participants will be enrolled in Cohort 5 with sabatolimab monotherapy.

For the randomization part (Cohort 3 and Cohort 4):

Following completion of screening procedures and prior to receive the first dose of study treatment, all eligible participants will be randomized via Interactive Response Technology (IRT) to one of the two cohorts: Cohort 3 with the combination sabatolimab + azacitidine or Cohort 4 with sabatolimab in monotherapy. The investigator or his/her delegate will contact the IRT after confirming that the participant fulfills all the inclusion/exclusion criteria. The IRT will assign a randomization number to the participant, which will be used to link the participant to a treatment and will specify a unique medication number for the first package of sabatolimab to be dispensed to the participant. Study treatment azacitidine will be supplied by Sponsor (global) or sourced locally for participants randomized in Cohort 3.

The randomization numbers will be generated using the following procedure to ensure that treatment assignment is unbiased and concealed from participants and investigator staff. A participant randomization list will be produced by the IRT provider using a validated system that automates the random assignment of participant numbers to randomization numbers. These randomization numbers are linked to the different treatment arms, which in turn are linked to medication numbers. A separate medication list will be produced by or under the responsibility of Novartis Global Clinical Supply (GCS) using a validated system that automates the random assignment of medication numbers to packs containing the study treatment.

The randomization scheme for participants will be reviewed and approved by a member of the Randomization Office.

6.4 Treatment blinding

Treatment will be open to participants, investigator staff, persons performing the assessments, and the CTT.

6.5 Dose escalation and dose modification

Two dose levels of sabatolimab, 400mg Q4W and 800mg Q4W will be evaluated. Intraparticipant dose escalation is not permitted at any time during the study. Guidance for dose modifications is provided in Section 6.5.

6.5.1 Dose escalation guidelines

Sabatolimab will be given at 400 mg IV every 4 weeks in the first cohort including approximately 8 participants (to obtain at least 6 evaluable participants). If there is no unacceptable level of toxicity during the first 2 cycles at this dose level, sabatolimab will be given at 800 mg IV every 4 weeks in the second cohort including approximately 12 participants (to obtain at least 9 evaluable participants).

The level of toxicity will be assessed by the number of dose-limiting toxicities as defined in Table 6-2.

Guidelines for dose escalation and for determination of the recommended dose for expansion are presented in Section 6.5.2.

In case of safety concerns and/or based on pharmacokinetic/pharmacodynamic data during the safety run-in part of the study (Part 1), the following changes may be considered:

- To include additional participants at the current dose level
- To not escalate to the next planned dose (sabatolimab 800 mg Q4W)

6.5.2 Guidelines for determination of the recommended dose for expansion (RDE)

The recommended dose for expansion (RDE) of sabatolimab will be the highest dose level between 400 mg and 800 mg Q4W that is not expected to cause an unacceptable level of toxicity (DLT) including aGvHD and cGvHD in more than 50% of the treated participants during the DLT evaluation period (See Table 6-2).

Notably, the curative efficacy of aHSCT is attributable to GvL, which inherently maybe associated with risk of GvHD, with reported incidence rates of clinically significant aGvHD ranging from 9% to 50%, and cGvHD from 30% to 70% (see Section 1.1). Therefore, post-

aHSCT immunomodulatory interventions, including sabatolimab, that promote GvL could potentially induce GvHD and other immune-related adverse events.

However, the assessment of whether GvHD or unacceptable level of toxicity is possibly treatment-related, and therefore a DLT, will be confounded by the inherent background incidence of GvHD associated with aHSCT. As the reported incidence of acute and chronic GvHD is similar to or in some cases higher than the standard threshold for incidence of DLT in phase I studies (i.e. DLT rate < 33.3%), a higher threshold (DLT rate of 50%) was selected for the Bayesian model to determine if sabatolimab given as monotherapy is not meeting an unacceptable level of toxicity.

However, all toxicities \geq grade 2 will be individually reviewed to evaluate safety data of each cohort from the Safety Run-in part.

In the first cohort, approximately 8 participants (to obtain at least 6 evaluable participants) will be treated with the starting dose of sabatolimab 400 mg every 4 weeks.

In the second cohort, approximately 12 participants (to obtain at least 9 evaluable participants) will be treated with sabatolimab 800 mg every 4 weeks.

For both cohorts, participants must complete a minimum of 2 cycles of treatment with the minimum safety evaluation and drug exposure or have had at least one dose-limiting toxicity (DLT) including aGvHD and cGvHD within the first 2 cycles of treatment to be considered evaluable for dose escalation/expansion decisions. Dose escalation/expansion decisions will occur when the cohort of participants have met these criteria.

Dose escalation/expansion decisions will be made by Investigators and Novartis study personnel (including the study physician and statistician) during a dose decision meeting by teleconference. Decisions will be based on a synthesis of all relevant data available from all dose levels evaluated in the ongoing study including safety information, incidence and severity of aGvHD and cGvHD, incidence of DLTs, all Common Terminology Criteria for Adverse Events (CTCAE) Grade ≥ 2 toxicity data during the first two cycles, available PK and PD data from evaluable participants.

The recommended dose for the next cohort of participants (second cohort in the safety runin part, expansion cohort, combination cohort and adolescent cohort) will be guided by a Bayesian logistic regression model (BLRM) and by applying the following principle: the risk to have $\geq 50\%$ DLTs including GvHD must be below 25%. This adaptive Bayesian methodology has the advantage to incorporate information gained at the preceding dose levels. Thus, additional participants may be enrolled at this dose level or a higher dose level as agreed by Investigators and Novartis personnel and if the BLRM predicts that the risk to have $\geq 50\%$ dose limiting toxicities (DLTs) including GvHD remains below 25%.

Sabatolimab administration at the next higher dose level (sabatolimab 800 mg Q4W) or starting the recruitment of the Part 2 of the study (monotherapy expansion cohort, combination cohort and adolescent cohort) may not proceed until the investigator receives written confirmation from Novartis indicating that the results of the previous cohort were evaluated and that it is permissible to proceed to open a new cohort.

6.5.3 Definitions of dose limiting toxicities (DLTs)

Dose-limiting toxicities will be collected and evaluated in participants enrolled to the Safety Run-in part and adolescent cohort.

A dose-limiting toxicity (DLT) is defined as an adverse event or abnormal laboratory value considered by the Investigator to be at least possibly related to sabatolimab as a single contributor that occurs during the DLT observation period [during the first 2 cycles, ie, Cycle 1 Day 1 (starting from the first infusion of sabatolimab) to the end of Cycle 2 of treatment with sabatolimab monotherapy in Safety Run-in] and meets any of the criteria included in Table 6-2. The National Cancer Institute Common Terminology Criteria for Adverse events (NCI CTCAE) version 5.0 will be used for all grading, except for GvHD (Harris et al 2016 for aGvHD and NIH consensus criteria for cGvHD). For the purpose of dose-escalation decisions, DLTs will be considered and included in the BLRM.

If a participant experiences a DLT (during the DLT observation period) then study treatment must be interrupted and may be permanently discontinued depending on the severity of the DLT. If the DLT (other than GvHD) resolves to CTCAE Grade 1 or baseline value, the participant may continue to receive study treatment following consultation with the Novartis medical monitor.

For aGvHD and/or cGvHD that meet DLT criteria, refer to Table 6-4 for study treatment interruption, re-initiation and/or discontinuation.

The investigator must notify the sponsor immediately of any unexpected CTCAE grade ≥ 3 adverse events or laboratory abnormalities.

Table 6-2 Criteria for Dose Limiting Toxicities (DLTs)

Toxicity	DLT Criteria					
DLTs considered related to gra	aft vs host disease (GvHD) by the Investigator assessment					
Acute GvHD	Grade IV acute GvHD					
	Stage ≥3 lower GI acute GvHD (consistent with Grade III acute GvHD)					
	Stage ≥3 liver acute GvHD (consistent with Grade III GvHD)					
Chronic GvHD	Moderate chronic GvHD of the lungs					
	Severe chronic GvHD					
Other DLTs excluding acute or	chronic GvHD by the investigator assessment					
Immune-related adverse events (irAEs)	- irAEs ≥ CTCAE Grade 3 persisting > 7 days after starting appropriate treatment (e.g. with corticosteroids)					
	- Pneumonitis ≥ CTCAE Grade 2 persisting > 7 days despite treatment with corticosteroids					
	- Pneumonitis ≥ CTCAE Grade 3					
Hematology	- Febrile neutropenia ≥ CTCAE Grade 3 in the absence of leukemic involvement in the marrow					
	- Thrombocytopenia ≥ CTCAE Grade 3 with clinically significant bleeding in the absence of leukemic involvement in the marrow					
	- Grade 4 neutropenia, thrombocytopenia, and pancytopenia, not related to leukemic infiltration, and do not respond to growth factor or transfusion support within 14 days will be considered to be a DLT (BM evaluation may be required to determine if marrow aplasia is due to leukemia).					
Infusion related reactions	Infusion reaction CTCAE Grade 3 that does not resolve to Grade 1 within 72 hours or CTCAE grade 4 of any duration.					

Toxicity	DLT Criteria
Other	Any other unacceptable non-hematological toxicity encountered by a participant as determined by the Investigators and Novartis.

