12.8 Sample size calculation

12.8.1 Primary endpoint(s)

Primary safety analysis (incidence of dose-limiting toxicity)

No formal statistical power calculations to determine sample size were performed for the safety run-in part.

A cohort of 6 to 8 participants will be enrolled in the first cohort treated with sabatolimab at 400 mg Q4W dose level and a cohort of 9 to 12 participants will be enrolled in the second cohort treated with sabatolimab at 800 mg Q4W dose level.

Table 12-1 presents different scenarios for the incidence of DLTs in the two cohorts of the safety run-in part and the decision made based on the Bayesian logistic regression model using weakly informative priors (with means corresponding to a risk of DLT at the reference dose of 15%, and a doubling in dose leading to a doubling in the odds of the risk of a DLT).

The 15% DLT rate corresponds to the anticipated intrinsic risk of GvHD in this post-transplant setting. Of note, no historical data has been considered in the Bayesian model as no participant was already treated with sabatolimab in this post-transplant setting.

In the context of this intrinsic risk of GvHD, the definition of an acceptable level of toxicity does not follow the EWOC criterion (i.e. probability to observe a DLT rate exceeding 33% is below 25%) as defined in a standard oncology phase I study. Thus, instead of considering a 33% threshold for the probability to observe a DLT rate, we will select 50% as the threshold to qualify for an acceptable toxicity (i.e. probability to observe a DLT rate exceeding 50% is below 25%).

Table 12-1 Probability of unacceptable toxicity for different hypothetical scenarios

Number of participar least one (including among ev participar	nts with at DLT g GvHD) valuable	Probability to observe a DLT rate with three different definition of over-toxicity (>40%, >45% or >50%)					
		DLT rate >	DLT rate >40%		DLT rate >45% DLT rate >50%		•50%
1st cohort 400 mg	2nd cohort 800 mg	Next dose*	P(excessive toxicity)	Next dose*	P(excessive toxicity)	Next dose*	P(excessive toxicity)

Number of participal least one (including among exparticipal	nts with at DLT g GvHD) valuable	Probability to observe a DLT rate with three different definition of over-toxicity (>40%, >45% or >50%)				tion of over-	
1/6		800	0.219	800	0.166	800	0.125
2/6		400	0.211	400	0.145	400	0.094
3/6		Stop		stop		stop	
2/8		400	0.094	400	0.055	800	0.216
3/8		stop		400	0.199	400	0.129
0/6	2/9	800	0.038	800	0.016	800	0.007

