16.6 Appendix 6: Statistical details on the Bayesian Logistic Regression Model (BLRM)

Statistical Models

The safety run-in part of this study to confirm that the sabatolimab is safe will be guided by a Bayesian analysis of dose limiting toxicity (DLT) data. The statistical model will be a Bayesian Logistic Regression Model (BLRM) consisting of a single agent dose-DLT component.

Let π (d) be the risk of DLT for sabatolimab given as a single agent Q4W at dose d. The single agent dose-DLT model is as follow:

 $logit(\pi(d)) = log(\alpha) + \beta log(d/d^*)$

where d*= 800 mg Q4W (reference dose of sabatolimab) is used to scale the doses of sabatolimab. Hence, α (>0) is the single-agent odd of a DLT at 800 mg Q4W; β (>0) is the increase in the log-odds of a DLT by a unit increase in log-dose.

Taking into account the intrinsic risk of GvHD (which is part of the DLT definition) in the posttransplant setting, we selected a weakly informative prior with means corresponding to a risk of DLT at the reference dose of 15%, and a doubling in dose leading to a doubling in the odds of the risk of a DLT.

No meta-analytic-predictive (MAP) approach was used to derive the prior distribution as historical data are not available in this post-transplant setting.

The prior distribution is specified in Table 16-9.

Table 16-9 Prior distribution

Parameter	Prior distribution		
μ1	N(mean = logit(0.15), sd = 2)		
μ2	N(mean = 0, sd=1)		

The recommended dose for expansion will be the highest dose between 400 mg and 800 mg Q4W for which the probability of excessive toxicity (i.e. DLT rate $\geq 50\%$) is less than 0.25.

The summary of prior distribution of DLT rates is specified in Table 16-10.

Summary of prior distribution of DLT rates **Table 16-10**

Dose of sabatoli mab	Prior probabilities that P(DLT) is in the interval: [0, 0.50) [0.50,1]		Mean	SD	Quantiles	;			
					2.5%	50%	97.5%		
400 mg Q4W	0.897	0.103	0.163	0.220	0.000	0.061	0.813		
800 mg Q4W	0.806	0.194	0.257	0.264	0.003	0.151	0.900		

Hypothetical on-study scenarios

To illustrate the performance of the BLRM used to guide the tolerability assessment in the safety run-in part for sabatolimab in monotherapy, hypothetical data scenarios are displayed in Table 16-11. Decision will be based on additional safety, PK or PD information.

Table 16-11 Probability of unacceptable toxicity for different hypothetical scenarios

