2.5.2 Statistical hypothesis, model, and method of analysis

Primary safety analysis in adults (safety run-in part only)

A Bayesian model will be used to assess whether sabatolimab at the two tested dose levels is not meeting an unacceptable level of toxicity in adults from the DDS. The threshold to qualify for an acceptable level of toxicity was higher (50%) than the standard threshold used in phase I study (33%) because:

- aGvHD and cGvHD are included in the DLT definition,
- Yet, the curative efficacy of aHSCT is attributable to GvL, which inherently maybe associated with risk of GvHD,
- Therefore, post-aHSCT immunomodulatory interventions, including sabatolimab, that promote GvL could potentially induce GvHD and other immune-related adverse events.

The relationship between the dose of sabatolimab and the probability of DLT is modeled using a logistic regression detailed in Appendix Section 16.6 of the protocol. A summary of the characteristics of this Bayesian model is presented below:

- A single agent dose-DLT logistic model will assess the toxicity risk of sabatolimab.
- Taking into account the lack of historical data and the intrinsic risk of GvHD (which is part of the DLT definition) in the post-aHSCT setting, a weakly informative priors with means corresponding to a risk of DLT at the reference dose of 15%, and a doubling in dose leading to a doubling in the odds of the risk of a DLT were selected.

Novartis	Confidential	Page 22 of 35
SAP – Amendment 1		CMBG453F12201

• The prior risk of excessive toxicity (i.e. risk of DLT within [50%-100%]) is 10.3% for the sabatolimab 400 mg Q4W and 19.4% for the sabatolimab 800 mg Q4W.

After each cohort in the safety run-in part, the posterior distribution for the risk of DLT for new participants at the dose level of interest will be evaluated. The posterior distributions will be summarized to provide the posterior probability that the risk of DLT for each dose level of sabatolimab lies within the interval [50%, 100%] (i.e. excessive toxicity). After the first cohort, if this posterior probability is less than 25% for the two dose levels (400 mg and 800 mg), it would be recommended to start enrolling participants in Cohort 2 with sabatolimab 800 mg Q4W dose level.

Primary safety analysis in adolescent (Cohort 5 only) - Not assessable

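### The single-contributor wording in the DLT definition conflicts with the GvHD-inclusive endpoint behind the 15% prior and the 50% limit, and one reclassified event can change the BLRM recommendation

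*Protocol*

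**What the plan says.** Protocol 6.5.3 sets two conditions that must both hold. The event must be "considered by the Investigator to be at least possibly related to sabatolimab as a single contributor", and it must meet a criterion in Table 6-2. That table lists five GvHD criteria: grade IV acute GvHD, stage 3 or higher lower GI acute GvHD, stage 3 or higher liver acute GvHD, moderate chronic GvHD of the lungs, and severe chronic GvHD.

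Elsewhere the plan treats GvHD as part of the count:

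- **Protocol 6.5.2** says that judging whether GvHD "is possibly treatment-related, and therefore a DLT, will be confounded by the inherent background incidence of GvHD associated with aHSCT". It also says that "a higher threshold (DLT rate of 50%) was selected for the Bayesian model", because reported GvHD incidence is similar to or above the usual 33.3% limit.
- **Protocol 12.8.1** gives the source of the prior: "The 15% DLT rate corresponds to the anticipated intrinsic risk of GvHD in this post-transplant setting".
- **Protocol 16.6** begins its choice of prior with "Taking into account the intrinsic risk of GvHD (which is part of the DLT definition").
- **SAP 2.5.2** gives as its first reason for the 50% limit that "aGvHD and cGvHD are included in the DLT definition".
- **SAP 2.5.1** takes the DLT definition from Table 6-2 and does not repeat the attribution clause.

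Neither document explains the single-contributor condition or says how GvHD with both graft and drug as possible causes is to be counted.

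**The concern.** The two halves of the clause pull in different directions. Possible relatedness is a low bar; being the only contributor is a high one. GvHD after an allogeneic transplant has the graft as a contributor, so an investigator who applies the second half could record a Table 6-2 GvHD event as not a DLT.

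The prior and the limit were set for a count that contains GvHD. If some GvHD leaves the count while the limit stays at 50%, the same rule, P(DLT rate ≥ 50%) < 25%, tolerates more toxicity than its rationale implies. If sites read the clause differently, the primary safety proportion also depends on local attribution practice in an open-label study. Protocol 2.1 names exacerbation of GvHD risk first among the matters the study is meant to settle.

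**Working it through.** **Inputs.** From Protocol 16.6: logit π(d) = log α + β log(d/800); log α ~ N(logit 0.15, SD 2); log β ~ N(0, SD 1). No correlation is stated, so zero is assumed. The rule recommends the highest dose with P(π ≥ 0.5) < 0.25. Cohort sizes are 6 to 8 at 400 mg and 9 to 12 at 800 mg (Protocol 12.8.1).

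**Reproducing the plan.** At 800 mg the log-dose term is zero, so the prior P(π ≥ 0.5) is 1 − Φ(−logit(0.15)/2) = 1 − Φ(0.867) = 0.193; Table 16-10 gives 0.194. At 400 mg numerical integration gives 0.103, as stated. All 14 scenario decisions at the 50% threshold in Table 12-1 reproduce, with probabilities within about 0.005. The BLRM arithmetic is sound; the question is which events enter it.

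**Moving one event, from Table 12-1 alone (50% threshold).**

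| Count | Recommendation | One fewer DLT | Recommendation |
|---|---|---|---|
| 3/6 | stop | 2/6 | 400 mg |
| 2/6 | 400 mg | 1/6 | 800 mg |
| 3/8 | 400 mg | 2/8 | 800 mg |
| 0/6 then 5/9 | 400 mg | 0/6 then 4/9 | 800 mg |
| 1/6 then 5/9 | 400 mg | 1/6 then 4/9 | 800 mg |

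**Recomputed P(π ≥ 0.5) at 800 mg.** 2/6: 0.33; 1/6: 0.13 (stated 0.125). With 1/6 at 400 mg, 5/9: 0.37; 4/9: 0.18 (stated 0.184); 3/9: 0.07 (stated 0.068).

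**The denominator.** The table above keeps the participant evaluable. Under Protocol 12.1, a participant without a DLT stays in the Dose-Determining Set only after two full infusions and at least 28 days of observation following the second. Table 6-4 interrupts or discontinues treatment for GvHD of this severity, so a participant whose event is set aside may drop out of the set. With 1/6 at 400 mg:

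- one event and its participant removed, 4/8: 0.26, so 400 mg is still recommended;
- two events and both participants removed, 3/7: 0.16, so 800 mg is recommended.

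Either case falls below the nine evaluable participants required, and Protocol 9.1.1.3 would then consider an additional enrolment.

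**Illustration of operating characteristics.** The documents do not give the share of events that would be set aside. Suppose a background GvHD rate b, independent of drug-caused DLTs, goes uncounted and participants stay evaluable. The counted rate is 1 − (1 − p)/(1 − b). For true all-cause rates of 40% and 50% with b = 15%, this is 1 − 0.60/0.85 = 29.4% and 1 − 0.50/0.85 = 41.2%. Exact enumeration, averaged equally over the allowed cohort sizes (the plan does not state its mix), gives:

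| Assumed b | P(stop) | P(expand at 800 mg) |
|---|---|---|
| 0 (Table 16-12: 0.377, 0.127) | 0.38 | 0.11 |
| 5% | 0.32 | 0.16 |
| 10% | 0.25 | 0.23 |
| 15% | 0.18 | 0.32 |
| 20% | 0.12 | 0.44 |
| 30% | 0.02 | 0.76 |

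**The case against.** The best defence is that nobody would read the clause so as to exclude GvHD. That reading would empty five rows of Table 6-2 and make possible relatedness pointless. The estimand, Protocol 6.5.2 and 16.6, and the SAP all treat GvHD as countable. The words could simply mean sabatolimab as the only study drug.

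Much of this stands. A reader might infer that the plan leaves GvHD out of the DLT count altogether; the documents do not support that, since the intention to include it is stated repeatedly. But the only-study-drug reading makes the words redundant: DLTs are collected only in the Safety Run-in and adolescent cohorts, where sabatolimab is already the only study drug. The text leaves an investigator free to read them as a condition on cause. Protocol 6.5.2 also retains an attribution step, so it does not say that every background case counts.

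A reader might also infer that the trial cannot detect worsening GvHD. That goes too far. The BLRM only guides the decision. Protocol 6.5.2 requires individual review of all toxicities of grade 2 or higher and lists GvHD incidence and severity separately from DLTs. SAP 2.7.1.1 lists grade III–IV acute and moderate to severe chronic GvHD without any attribution condition. These safeguards reduce the risk but do not correct the DLT count or the reported primary proportion.

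Two further limits stand. The number of events set aside in any example is hypothetical, and, as the 4/8 case shows, one reclassified event does not always change the recommendation. Also, recruitment has been halted, so changing the wording now alters no enrolment decision.

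**Conclusion.** The concern holds as an unresolved contradiction about attribution. The single-contributor condition does not match the endpoint for which the prior and the 50% limit were set, and to the extent that it is applied as worded the rule is more permissive than its stated rationale. One or two reclassified events can change the recommended dose, conditional on who remains evaluable. The operating-characteristic figures are a range under an assumed background rate. The 15% value should not be read as a measured GvHD rate: it is the centre of a wide prior at 800 mg, where Table 16-10 gives a mean of 0.257, against a median of 0.061 at 400 mg. Nothing in the documents shows that any event was set aside or that a dose decision was affected.

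The point still matters for reporting. SAP Table 1-1 keeps the adult DLT endpoint in the final CSR, while SAP 2.5.5 and 2.5.6 plan no sensitivity or supportive analysis.

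**What to change.** Reconcile Protocol 6.5.2, 6.5.3, 12.8.1 and 16.6 and SAP 2.5.1 and 2.5.2 on one attribution rule for GvHD that matches the endpoint assumed by the prior and the 50% limit. A DLT also triggers mandatory treatment interruption under 6.5.3, so simply striking the words would change a clinical rule. Which rule is right is for the sponsor and investigators to settle.

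In SAP 2.5, add a supportive DLT proportion and one BLRM run that count every Table 6-2 event in the DLT window regardless of attribution. For that run, the Dose-Determining Set should include any participant with such an event even if the minimum exposure criterion is not met; otherwise the participants of most interest could drop out.

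The cost is a wording reconciliation and one extra analysis, drawing on the adverse events and GvHD grading that the protocol already has sites record. The supportive DLT rate may be higher than the primary one, and it should be labelled as a different endpoint.
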